2.2 Secondary Objectives

Secondary Objective: Our secondary objective is to assess the impact of switching from rituximab to ocrelizumab (**only in the switching group**) on the incidence and prevalence of anti-drug antibodies to ocrelizumab. The presence of anti-drug binding antibodies will be assessed prior to the first and third ocrelizumab infusion and six to twelve months after the last ocrelizumab infusion. The serum drawn before the first infusion of ocrelizumab will be the baseline comparator since these patients will only have been exposed to at least two rituximab infusions over 6 months with no prior exposure to ocrelizumab. This means we will have 100 serum samples prior to ocrelizumab exposure and 200 after ocrelizumab exposure. These assays will be performed by PPD Bio A

Laboratories (in Richmond, VA) who will assess the anti-drug antibodies to ocrelizumab”, and “QPS (Netherlands) who will assess the anti-drug antibodies to rituximab as a single batch once all samples have been collected and cryopreserved.

Other secondary objectives that will be assessed in **the switching group** only include the following:

- a. We will assess the percent of ocrelizumab treated patients that exhibit early recovery of CD19+ and/or CD20+B cells (>1%) prior to each ocrelizumab infusion and at month 12 or 18 which is 12 or 18 months following the first infusion of ocrelizumab. We will compare this to the percent of patients with evidence of early recovery from rituximab as assessed by the baseline B cell panel. Our test will also identify CD19 antigen expression to confirm depletion since presence of anti-CD 20 MAB in patients blood may confound the CD-20 expression assay.
- b. We will assess cytokines to evaluate for possible contribution of a cytokine storm to infusion reactions. Cytokines will be assessed using the MesoScale platform. These blood samples will be collected before the start of each ocrelizumab infusion and following infusion completion. Blood samples will also be collected during a moderate or serious IRR.
- c. We will describe all adverse events and serious adverse events in addition to IRRs (for example infections) as described in the investigator’s brochure.

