3.2 Rationale for Study Design

Ocrelizumab and rituximab are among the most effective disease modifying therapies studied to date. Also, their safety profile to date (in terms of serious adverse events) is better than the other highly effective therapies including natalizumab, fingolimod, alemtuzumab, daclizumab and dimethyl fumarate. Several centers including the RMMSC and the Swedish Coalition of MS Clinics have large MS populations on rituximab, some for more than 6 years. However, rituximab does not have a patient assistance program, will remain off label for MS and will have significant uncertainty about access for the seeable future. Also, Ocrelizumab has been positioned to possibly be superior to rituximab in terms of IRRs, ADA and efficiency of B cell depletion. Although, these statements have not been proved, they will be influential to some MS patients, rituximab prescribers and third party payers. Thus a significant amount of

switching from rituximab to ocrelizumab is likely to occur. We know of no data describing the consequence of such switching in terms of IRRs, formation of ADAs and efficiency of B cell depletion. The proposed study has good power to address these 3 issues. It is not powered to look at any efficacy outcomes and none are included. We will monitor for safety per standard operating procedures for our study team.

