3.3.2 Secondary Outcome Measures

- a. Anti-drug antibodies (ADAs): We will measure the number of patients who have treatment induced ADAs against rituximab and ocrelizumab prior to every ocrelizumab infusion (T_0 , T_1 , T_2) and at the research termination visit (T_3 =between month 12 and 18) in **ONLY** the switching group. This analysis will be performed by PPD Bio A Laboratories (in Richmond, VA) who will assess the anti-drug antibodies to ocrelizumab, and “QPS (Netherlands) who will assess the anti-drug antibodies to rituximab a single batch at end of study for the switching group.
- b. Treatment efficiency: We will measure B cell depletion before each ocrelizumab infusion (T_0 , T_1 and T_2), by the clinical laboratories (T cell and B cell panel) at the University of Colorado Hospital. We will measure the proportion of patients who are B cell depleted (CD-19+ and CD-20+) by the time of the next infusion and 6 to 12 months after the last infusion in the switching group.
- c. Cytokine profile: To better characterize infusion reactions and evaluate the contribution by either hypersensitivity reactions to ocrelizumab directly and/or by release of cytokines from dying CD20 positive cells, serum levels of cytokines will be evaluated. Cytokines will be measured using the MesoScale platform before the start of each ocrelizumab infusion, and after the infusion is completed (T_0, T_1, T_2, T_3). In addition, blood samples will be collected for those who experience a moderate to severe IRR to further examine cytokine profiles during an IRR. Plasma samples will be analyzed using the V-PLEX Human Biomarker 40-Plex Kit which assays for IFN- γ , IL-1 β , IL-2, IL-4, IL-6, IL-8, IL-10, IL-12p70, IL-13, TNF- α , GM-CSF, IL-5, IL-16, IL-7, IL-12/IL-23p40, IL-1 α , VEGF-A, IL-17A, IL-15, TNF- β , IL-8 (HA), MCP-1, MCP-4, Eotaxin, IP-10, MDC, Eotaxin-3, TARC, MIP-1 α , MIP-1 β , VEGF-C, VEGF-D, Tie-2, Flt-1/VEGFR-1, PIGF, FGF (basic), SAA, CRP, VCAM-1, ICAM-1 per manufacturer’s recommendation on a MesoScale SECTOR Imager 2400. This array of cytokines will provide information on the levels of cytokines being released during the infusion to determine if they are limited to those released by B cells. Patients will be categorized as either not having had an IRR (Grade 0), having had a mild

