4.9.4 Safety Analysis

The default analysis will be available case for all eligible participants on an intent to treat basis. Alpha = 0.05 for all tests. As in the OPERA I and II randomized clinical trials, the primary and secondary end points will be descriptively presented. Frequencies and percentages for the severity of IRR grades (Grades 0-5) will be presented for both study groups following each infusion time point and overall between groups. 95% confidence intervals for the proportions will be calculated. Differences in the distribution of IRR severity grades between independent samples (i.e. comparison between groups at a common time point) will be tested with the chi-square or Fisher's exact association test, and additionally with ordinal or multinomial logistic regression. If sample sizes are small among some levels of IRR severity grades, they may be collapsed or dichotomized (i.e. Grade 3 or higher, any reaction or no reaction, severe reaction or none as examples) and methods described for binary outcomes under secondary endpoints will be utilized. Dichotomization may be used to make analysis and presentation of results more manageable as well.

The primary endpoint will be the proportion of whether any IRR occurred (yes or no) per infusion cycle per patient in each study group. The secondary endpoints include the proportion per infusion per patient of severe infusion reaction (grade 3 or greater), the proportion of infusion reactions and severe infusion reaction per patient across all infusions, the proportion patients with anti-drug antibodies, and the proportion of patients with depleted B cells. The primary outcome, binary occurrence of IRR per infusion per patient, could be analyzed with logistic or relative risk models, with GEE (generalized estimating equations) and/or GLMM

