4.9.6 Determination of Sample Size

The sample size will be a convenience sample. It is anticipated a minimum of 100 patients will qualify for each cohort (200 total) resulting in studying 300 infusions with ocrelizumab and 200 infusions with rituximab. This is an observational study not designed to demonstrate superiority of ocrelizumab over rituximab in efficacy but instead indicate the magnitude of the relative tolerability and immunogenicity. The primary endpoint is the difference in the percentage of IRRs between the two study groups. In addition, both study groups will include treatment experienced patients on rituximab who have experienced a minimum of two infusions and either continue to stay on rituximab or switch to ocrelizumab.

To estimate study power with the proposed sample size of 100 infusions in each group, we conducted a chart review of 50 patients at the Rocky Mountain MS Center who are currently taking rituximab and examined their IRRs using the proposed IRR grading scale (see section 3.3.1) from Grade 0-5. The number and severity of IRRs were captured following their third rituximab infusion. The highest grade of an IRR that occurred during the infusion was recorded. Our pilot data revealed that following the third rituximab infusion, 14.3% of patients had an IRR of which 85.71% were Grade 0, 12.24% were grade 2 and 2.05% were Grade 3. Hauser et al., found that following the second infusion of rituximab in patients, the majority of whom (60%) were not taking a DMT for 6 months prior to initiating rituximab only 20.3% experienced in an IRR.³

Using IRR estimates from our pilot data and establishing a clinically meaningful difference of 20% increase in IRRs, we conducted the following power analysis for a sample of 95 patients (assuming a 5% attrition rate after recruiting 100 patients in each study group). An IRR proportion for ocrelizumab users at 34.3% compared with 14.3% for rituximab (obtained from our pilot data) for a two sided (alpha = 0.05) two sample proportion test for the null hypothesis of no difference between rituximab and ocrelizumab in proportion of IRRs would result in 90% power for 95 patients per group.

In response to the FDA IND letter, “the power analysis in Section 4.9.6 of the protocol appears to compare the infusion-related reaction (IRR) rate at the third rituximab infusion (14.3%) to that of the first infusion of OCR (34.3%). Because

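### B-cell depletion is measured as a percentage in the same patients before and after the switch but analysed only at the 1% cut; a prespecified paired analysis of the percentage should sit beside the proportion

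*Combined protocol and SAP*

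**What the plan says.** Section 4.5.1 and Table 1 have B- and T-cell subsets measured by flow cytometry in the switching group at T0 (on rituximab, before the first ocrelizumab infusion), T2 (6 months) and T3 (months 12-18). The raw data are therefore quantitative and paired.

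Every statement of the outcome is a share of patients:

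- The Introduction defines depletion as at or below 1% and hypothesises that the proportion depleted after switching will not differ from baseline.
- Section 2.2a: "We will assess the percent of ocrelizumab treated patients that exhibit early recovery of CD19+ and/or CD20+B cells (>1%) prior to each ocrelizumab infusion", compared with the baseline panel.
- Section 3.3.2b: "We will measure the proportion of patients who are B cell depleted (CD-19+ and CD-20+) by the time of the next infusion".
- Section 4.9.4 lists "and the proportion of patients with depleted B cells" among the secondary endpoints and sends longitudinal binary outcomes to GEE or GLMM, with "Alpha = 0.05 for all tests".

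The paired t-test in 4.9.4 is assigned to cytokine markers, and the signed-rank test is named as its substitute. No analysis of the B-cell percentage as a quantity is planned.

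Section 3.2 names efficiency of B-cell depletion as one of three questions and states: "The proposed study has good power to address these 3 issues". The sample-size section (4.9.6) calculates power for infusion-related reactions only.

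**The concern.** Cutting a measured percentage at 1% discards how far a patient is below the cut and how far above it a recovering patient has risen. If few patients are above 1%, the paired comparison rests on the few who cross the line between visits.

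The direction of the hypothesis makes this matter. The plan expects no change and sets no equivalence margin for B cells. A comparison with little power tends to return the expected answer, and the statement in 3.2 invites the reader to trust it. At stake is whether the study can detect, and put a size on, a change in depletion after the switch.

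**Working it through.** **1. The plan's own power figure.** Section 4.9.6 uses a "two sided (alpha = 0.05) two sample proportion test" with "An IRR proportion for ocrelizumab users at 34.3% compared with 14.3% for rituximab" and concludes that this "would result in 90% power for 95 patients per group". With mean proportion 0.243:

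z = [0.20 × √95 − 1.96 × √(2 × 0.243 × 0.757)] / √(0.343 × 0.657 + 0.143 × 0.857) = (1.949 − 1.189) / 0.590 = 1.29, so power is 90.1%.

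The figure reproduces, but it concerns infusion reactions. There is no B-cell figure to reproduce.

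**2. What the binary comparison rests on.** With 95 pairs (100 recruited less the plan's 5% attrition), a change between 10% and 5% above the cut is a net 0.05 × 95 = 4.75 patients. In an exact paired (McNemar) test, five patients all moving the same way give p = 2 × 0.5⁵ = 0.0625, and six give 2 × 0.5⁶ = 0.031. At least six one-way movers are needed, and any movement in the other direction raises that number.

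**3. Assumptions.** The documents give no share above 1%, no SD and no before/after correlation. Assumed: recovery shares of 5-20%, correlation 0.3-0.6, 0-75% of values at the assay limit, two-sided 0.05. Exact McNemar on one before/after pair stands in for the planned GEE or GLMM.

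**4. Scenario A: the whole distribution of log CD19+ shifts.** Simulated power, 95 pairs:

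| Share above 1% | Binary (McNemar) | Signed-rank on the percentage |
|---|---|---|
| 5% to 10%, or 10% to 5% | about 17-24% | about 40-97% |
| 10% to 20% | about 46-58% | about 73-100% |

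A separate calculation used 100 pairs and a shift of 0.3 SD towards deeper depletion. The paired t-test has noncentrality √100 × 0.3/√(2(1 − ρ)). At ρ = 0.5 this is 3.0, giving 84% power; over ρ = 0 to 0.7 the range is 56-97%. McNemar power is about 6% at a baseline share of 5%, 14-18% at 10%, 22-36% at 20% and 28-47% at 30%. At ρ = 0.5, baseline share 10-20% and 50-70% of values at the assay limit, the analysis of the percentage falls to 45-63%, against 16-32% for the binary test. With 85-90% of values at the limit, the gain in scenario A is about 6-39 points.

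**5. Scenario B: only the share above 1% changes.** Values among depleted patients vary but do not shift (assumed log10 mean −1, SD 0.4), 95 pairs:

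| Share above 1% | Binary (McNemar) | Signed-rank on the percentage |
|---|---|---|
| 5% to 10% | 19-24% | 11-21% |
| 10% to 20% | 45-59% | 30-48% |
| 20% to 5% | about 87-96% | about 59-87% |

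Here the binary test is as good or better. If every non-recovered patient sits exactly at the assay limit, the two are close: 17% v 21% for 5% to 10%, and 40% v 39% for 10% to 20%.

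**6. Reading.** Which analysis has more power depends on the form of the change, and the documents do not say which form to expect.

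**The case against.** The case for leaving the plan alone has real weight. The 1% cut is the protocol's own definition, and early recovery is a question about a share of patients. A shift among patients who all stay depleted would not answer it. Section 3.1 lists B-cell reconstitution among exploratory outcomes (although 2.2 and 4.9.4 treat it as secondary). Section 4.9.4 promises descriptive presentation with 95% CIs for proportions, which would show imprecision. A GEE or GLMM using T2 and T3 together may gain some power over the single pair used here. All of this stands, and it is why the proportion should stay.

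Two stronger readings are tempting, and the documents support neither.

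- A reader might infer that a real change will probably be missed. That depends on the baseline share, the size of the change and the correlation, none of which is given. A low baseline share cannot be taken from the Introduction, because its account of complete and sustained depletion comes from ocrelizumab trials. T0 is on rituximab, at least 6 months after the last dose under 4.1.2, and 4.3.1 acknowledges insurance delays and early B-cell recovery. A higher share raises the power of the binary test.
- A reader might infer that the continuous analysis should become the main B-cell comparison. Scenario B shows that the signed-rank test can lose substantial power when only a subset recovers.

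What the objection does not remove is that no paired analysis of the measured percentage is planned, and that the statement in 3.2 has no B-cell calculation behind it.

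**Conclusion.** The point holds as a gap in a secondary analysis. Analysing only the 1% dichotomy leaves the study weak against a shift in the whole CD19+ distribution when recovery is uncommon: about 17-24% power, against about 40-97% for a paired test, for 5% v 10% or 10% v 5% in 95 pairs. It does not leave the study weak against a large change in the share above 1%: about 87-96% power for 20% v 5%. The two analyses answer different questions and complement each other.

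The ranges rest on assumed shares, correlations and assay-limit fractions, with exact McNemar as the stand-in for the planned model. The primary endpoint and its 90% power figure are not affected.

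**What to change.** In 3.3.2b and 4.9.4:

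1. Keep the proportion at or below 1% as the protocol-defined endpoint, and report the paired difference from T0 to T2 and from T0 to T3 with a 95% CI.
2. Add a prespecified within-patient analysis of CD19+ percentage over the same intervals, with a 95% CI. Use either a mixed model on log CD19+ with values below the assay limit treated as left-censored and days since the last infusion as a covariate, or the Wilcoxon signed-rank test with a Hodges-Lehmann estimate.
3. State that p > 0.05 on the proportion will not be read as showing that depletion is unchanged.

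In 3.2, give a calculation for B-cell depletion or remove that question from the power statement.

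The sampling times also need reconciling before the analysis is written: 3.3.2b lists pre-infusion B-cell measurement at T0, T1 and T2, whereas 4.5.1 and Table 1 list T0, T2 and T3.

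The cost is small. The values are already being measured, so this is plan wording and one more secondary analysis. The downside is that below-limit values need a censoring or rank method, so the assay limit has to be recorded.

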Finally, IRRs have been hypothesized to be a reaction by autoantibodies to the treatment drug or possibly from the release of cytokines from CD20 expressing cells as they are destroyed by ocrelizumab causing a “cytokine storm”. Understanding this process may lead to mechanisms that may aid in ameliorating these infusion reactions. If they are associated with ADA, then it might be possible to predictively premedicate these patients only. Alternatively, if they are associated with cytokine release, it may be possible to eliminate premedication in patients who are already CD20⁺ cell depleted in subsequent infusions. Therefore, we will assay the profile of certain cytokines in the serum 4 hours after start of ocrelizumab infusion.

Since ocrelizumab has entered the market, third party payers within and outside the US have required that the FDA or EMA approved versions of anti-CD20 monoclonal antibodies be used in the treatment of MS, namely ocrelizumab. Currently, we estimate several thousand MS patients in the US and Sweden are taking rituximab currently. Thus, it will be important to demonstrate that switching from a chimeric anti-CD20 to a more fully humanized anti-CD20 does not lead to unexpected infusion reactions and does not increase the probability of development of anti-drug antibodies.

The Rocky Mountain MS Center (RMMSC) at the University of Colorado Anschutz Medical Campus prescribed rituximab infusions for 533 MS patients in the last 12 months, of which 323 patients received their infusion at the University of Colorado Hospital's Outpatient Infusion Center between September, 2015-March, 2016. The RMMSC is one of the few sites nationwide with large numbers of MS patients treated with rituximab. On March 28, 2017, Ocrevus (ocrelizumab) was approved by the FDA for the treatment of primary progressive and relapsing multiple sclerosis. With the approval of ocrelizumab, current rituximab users are being counselled by their MS providers at RMMSC to consider switching to ocrelizumab if it is the only anti-CD20 MAB covered by their insurance.

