reaction (Grades 1-2), or a moderate/severe reaction (Grades 3-5). These patient groups will also be evaluated for difference before and after their infusions for changes in each of the above cytokines. These groups of patients will also be evaluated for the presence of antibodies to ocrelizumab as described above.

- d. Patient reported infusion tolerance: A short patient reported outcome scale describing the patient's experience to any IRR during the ocrelizumab infusion developed by the research team at RMMSC. will be administered by the study coordinators at the end of each infusion. Scale items will measure patient responses to their perception and experience of IRRs.

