monitored through standard of care assessments for this population to include a complete metabolic panel (CMP) and complete blood counts (CBC) with differential. Second, their immune profile will be evaluated through an immunoglobulin panel and analyzing T and B cell subsets using flow cytometry by the clinical laboratories at the University of Colorado Hospital. Samples for the cytokine analysis will be drawn on a similar schedule. For the cytokine analysis, blood samples will be collected prior to and after each infusion in CPT tubes. Because moderate to severe infusions reactions can delay infusions, we will plan to add an additional blood draw when these reactions are detected to keep timing of the blood draws more consistent and to capture any possible peak in cytokine levels during these reactions should they be occurring. Plasma will be derived by centrifuging at 1500g for 15 min and then will be aliquoted and stored at -80C. Cells will be reconstituted in freezing media (20% fetal bovine serum, 10% DMSO) and stored at -80C for further analysis. Additionally, plasma samples will be analyzed by MesoScale SECTOR Imager 2400 for evaluation of cytokine levels. Blood draws for the anti-drug antibody analysis will also be drawn at T₁ and sent to PPD Laboratories, Richmond, VA using cryopreserved blood samples as a single batch at the end of the study and analyzed for cytokine analysis.

Patients will receive 100 mg of methylprednisolone 30 minutes before administration of ocrelizumab at each infusion cycle (T₀-T₂). Following the infusion, nursing staff will record IRR using the National Cancer Institute's Common Terminology for Adverse Events Scale. Patient self-assessment of IRRs will also be captured. Adverse events will also be recorded as described in Section 5 by either the nursing staff or study coordinators. Finally, at the last research termination visit (T₃), only blood samples, AEs and concomitant medications will be collected from study patients. Concomitant medications include those used for the treatment for spasticity, depression, or fatigue and other prescription and non-prescription concomitant treatments that will be captured from the patient directly.

Patients will then receive ocrelizumab or rituximab, if they wish, as ongoing therapy. Ocrelizumab and infusion costs will be provided by Genentech until ocrelizumab is approved by the FDA and available to the patient through their insurance plan.

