(generalized linear mixed models) methods to incorporate correlation on repeated infusions on a patient. The same method will apply to other longitudinal binary outcomes. Poisson or negative binomial models with exposure terms could calculate rates of IRR per infusion per patient as a counting process. Similar methods will be used to compare IRR rates between the switching group and OPERA I and II phase 3 clinical trials. The total number of IRRs experienced in each patient, will be analyzed with Poisson or negative binomial models. Paired T tests will be used to assess differences in specific cytokine markers between pre and post infusion at each infusion cycle. Patient reported outcomes will also be reported descriptively. Frequencies and proportions will be reported for adverse and serious events and loss to follow up

As contingency methodology, exact tests and confidence intervals for measures of association between categorical variables can be utilized when necessary, if the sample sizes for some of the cells are small. Transforms or rank based methods, such as Wilcoxon sign rank, can be used in place of the T-test if deviation for normality is severe. Otherwise the T-test is a robust test of mean differences for medium to large sample sizes. If matching leads to good balance between the treatment groups on the demographic and disease variables, including age, MS disease duration, and baseline PDDS score, then confounding will not be an issue and the proposed unadjusted tests should be adequate. Alternatively, if the demographic and disease variables are not balanced, then regression or propensity score methods will be used to adjust for potential confounding. Sensitivity analysis comparing unadjusted and adjusted results will be used to determine the extent of the confounding effect. Adjustment for covariates can sometimes improve the precision of the estimated treatment difference by reducing random noise in the outcome.

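### The only cytokine test named in section 4.9.4 is a pre/post paired t test that does not use IRR status; the plan should name a between-group analysis of cytokine change by IRR

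*Combined protocol and SAP*

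**What the plan says.** Section 2.2 gives the aim: "We will assess cytokines to evaluate for possible contribution of a cytokine storm to infusion reactions". The Introduction has the same question in mind when it sets cytokine release against anti-drug antibodies as possible causes of IRRs.

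Section 3.3.2 sorts switching-group patients into Grade 0, Grades 1-2 and Grades 3-5, and adds: "These patient groups will also be evaluated for difference before and after their infusions for changes in each of the above cytokines". It names no test, model or contrast.

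Section 4.9.4 names the test, to be run at each infusion cycle: "Paired T tests will be used to assess differences in specific cytokine markers between pre and post infusion". The general fallback in the same section, "Transforms or rank based methods, such as Wilcoxon sign rank, can be used in place of the T-test", changes the distributional assumption but not the pre/post contrast. Section 4.9.4 does not take up the evaluation by grade.

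Three design facts bear on the reading:

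- Cytokines are sampled in the switching group only (section 2.2).
- Section 4.5.1 states: "Patients will receive 100 mg of methylprednisolone 30 minutes before administration of ocrelizumab at each infusion cycle". Nothing says whether the pre-infusion sample is taken before or after the steroid.
- The Introduction says "we will assay the profile of certain cytokines in the serum 4 hours after start of ocrelizumab infusion", whereas sections 2.2 and 3.3.2 place the second sample after the infusion is completed. Section 4.5.1 adds a draw during moderate to severe reactions, both to keep timing more consistent and to catch a peak. The sentence opens "Because moderate to severe infusions reactions can delay infusions".

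**The concern.** Whether cytokine release contributes to IRRs is a question about association: do infusions with a reaction show a larger cytokine change than infusions without one? A paired test asks something else, namely whether the average change over everyone tested differs from zero. It can be positive with no link to IRRs and negative when a link exists.

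The grade groups in section 3.3.2 do not settle the matter. Read together with section 4.9.4, the most natural way to carry out the plan is a paired test inside each group. The groups will be very unequal in size, so a marker could be significant in non-reactors and not in reactors, or the reverse, through sample size alone. The grouping is also by patient, while IRR status can change from one infusion to the next. The plan does not say which status applies at a given infusion.

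At stake is the statement about mechanism. The Introduction would use it to inform thinking about who needs premedication, so a shift common to all patients should not be reported as evidence that cytokines drive reactions.

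**Working it through.** **Figures in the plan.** There is no power figure for the cytokine analysis. The only one is 90% for the primary IRR comparison (34.3% v 14.3%, 95 per group, two-sided 0.05; section 4.9.6). It reproduces: [0.200 − 1.96 × √(2 × 0.243 × 0.757/95)] / √[(0.343 × 0.657 + 0.143 × 0.857)/95] = (0.200 − 0.122)/0.0605 = 1.29, which is 90.1%. It says nothing about cytokines.

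**Inputs.** From section 4.9.6: n = 95 after attrition, 300 ocrelizumab infusions, IRR rates of 14.3% and 34.3%, and a pilot Grade 3 rate of 2.05% (on rituximab). From section 4.9.4: alpha 0.05. Assumed: effect sizes in SD of the (log) change, because the documents give none.

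**1. Common shift, no link to IRRs.** With 95 pairs, the paired test has 80% power at 0.29 SD. Simulation (5,000 runs, SD of change 1, shift 0.4 SD in everyone):

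| IRR rate | Paired test significant | Change by IRR status significant |
|---|---|---|
| 14.3% | 97% | 5% |
| 34.3% | 97% | 5% |

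**2. Real link, no average shift.** Reactors change by 0.8 SD more than non-reactors, and a common fall of 0.8 × IRR rate brings the overall mean change to zero:

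| IRR rate | Paired test significant | Change by IRR status significant |
|---|---|---|
| 14.3% | 5% | 76% |
| 34.3% | 5% | 95% |

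**3. Separate paired tests by group, identical change of 0.4 SD.** Power comes from the noncentral t with noncentrality 0.4√n.

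- IRR rate 14.3% (95 × 0.143 ≈ 14 reactors, 81 non-reactors): noncentrality 1.50 and 3.60, power 28% and 94%.
- IRR rate 34.3% (95 × 0.343 ≈ 33 and 62): noncentrality 2.30 and 3.15, power 61% and 87%.

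The same change would often be significant in one group and not in the other.

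**4. Grades 3-5.** At 2.05% (a rituximab figure, carried over as an assumption), 100 × 0.0205 ≈ 2 cases per 100 infusions and 300 × 0.0205 ≈ 6 over the study. That is too few for more than description.

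**5. Precision of the direct comparison.** Detectable difference at 80% power ≈ 2.80/√(n₁n₀/N).

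- 300 infusions treated as independent, IRR rate 34.3%: 2.80/√(102.9 × 197.1/300) = 0.34 SD.
- 300 infusions, IRR rate 14.3%: 2.80/√(42.9 × 257.1/300) = 0.46 SD.
- One infusion, n = 95 (exact t): 0.61 SD at 34.3% and 0.83 SD at 14.3%.

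The ocrelizumab rates by infusion in the Introduction (27.5% on Day 1, 4.71% on Day 15, 13.7% after Dose 2) average 45.91/3 = 15.3%. That is near the lower end of the range, where the detectable difference is larger. The Day 15 rate would give only about 95 × 0.0471 ≈ 4 or 5 reactors. Both facts favour pooling over infusions and adjusting for infusion number.

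**The case against.** The strongest reply is that section 3.3.2 already plans to look at cytokine change by IRR grade, and that its wording can be read as a comparison of change between groups. That stands as to intention: a reader might infer that the plan never meant to relate cytokines to IRRs, and the documents do not support that. What is missing is a named contrast. The one test that is named does not supply it.

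A paired test also has a proper use. Section 3.3.2 asks which cytokines are released during the infusion, and a pre/post summary at each cycle describes that. It belongs in the report as description.

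Three stronger readings are tempting and go too far.

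- *Every pre/post shift contains the steroid effect.* This depends on whether the first sample precedes the steroid, which is not stated, and the size of any effect cannot be computed from the documents. Elapsed time remains as a possible common cause in either case.
- *Reactors are sampled later, so the comparison is biased.* The plan foresaw delay and added a reaction draw to limit it, and a Grade 1 reaction does not call for interruption. What remains is that no analysis says how the extra draw is used. Grade 2 reactions may involve interruption yet are grouped as mild in section 3.3.2, so it is not clear that they trigger it.
- *The two post-sample times are incompatible.* The 300 mg infusion takes about 2.5 hours and the cannula stays in for at least another hour (section 4.3.1). A draw 4 hours after the start would therefore follow a routine 300 mg infusion. The texts need reconciling, but for that dose they can describe the same sample.

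Finally, section 3.1 calls the cytokine work exploratory, and the list of secondary endpoints in section 4.9.4 omits it. That limits the weight of the point.

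**Conclusion.** The point holds in a limited form. The aim and the evaluation by grade are in the plan, but the only cytokine test in section 4.9.4 does not use IRR status and cannot show whether cytokine change is linked to reactions. With 95 patients, a common shift of 0.4 SD would be significant in 97% of analyses with no link to IRRs, while a 0.8 SD link could pass unseen if a common fall offsets it. Separate paired tests by grade group would show different significance for the same change (94% v 28% power at a 14.3% IRR rate).

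These figures rest on assumed effect sizes and show what the test can and cannot distinguish. They do not estimate any actual steroid or timing effect. The precision range of 0.34 to 0.46 SD treats 300 infusions from about 100 patients as independent and assumes none is missing, so it is optimistic. No primary conclusion is affected. The change is worth making because it is cheap and because draw times that are not recorded cannot be reliably recovered later.

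**What to change.** In section 4.9.4, name the main cytokine analysis as a comparison of log(post/pre) between infusions with any IRR and infusions with none, using IRR status at that infusion. Adjust for log baseline and infusion number, and pool over infusions with GEE or a patient random effect, both of which section 4.9.4 already uses for repeated infusions. Report Grades 3-5 descriptively. Keep the paired tests, labelled as descriptive.

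Record the actual time of each draw relative to infusion start and to the steroid. Use draw time as a sensitivity adjustment only: delay may be a consequence of the IRR, and adjusting for it in the main model could remove part of the association sought. State how the extra reaction draw is used, for example as a separate descriptive summary.

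Reconcile the post-sample time between the Introduction and sections 2.2 and 3.3.2. The same edit can settle whether cytokines are drawn at T3, which section 3.3.2 lists and Table 1 does not.

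The cost is a paragraph of analysis text, time stamps on the sample record and a little more analysis work, with no new assays. The direct comparison is less precise than the paired test (about 0.34 to 0.46 SD over all infusions before clustering, against 0.29 SD for 95 pairs), but it addresses the stated question. If reconciliation changes when a sample is drawn, that is a protocol change and not only analysis wording.
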